1 PROTOCOL SUMMARY

1.1 Synopsis

Protocol Title: A Phase I, Double-Blind, Randomized, Multicenter Trial of the Safety, Tolerability, and Immunogenicity of V114 in Healthy Japanese Infants

Short Title: Safety and Immunogenicity of V114 in Healthy Japanese Infants

Acronym: Not applicable

Hypotheses, Objectives, and Endpoints:

There is no formal hypothesis in this study.

The following objectives and endpoints will be assessed in healthy Japanese infants.

Primary Objectives	Primary Endpoints

Objective: To describe the safety and tolerability profiles of V114 given subcutaneously (V114-SC) and V114 given intramuscularly (V114-IM) in healthy infants.	
Solicited injection-site adverse events (AEs) during Day 1 to Day 14 postvaccinationSolicited systemic AEs during Day 1 to Day 14 postvaccinationVaccine-related serious adverse events (SAEs) during Day 1 to 1 month post-Dose 4 (PD4)
Secondary Objectives	Secondary Endpoints

Objective: To assess the anti-pneumococcal polysaccharide (PnPs) serotype-specific Immunoglobulin G (IgG) response rates (proportion of participants meeting serotype-specific IgG threshold value of $\geq 0.35 \mu\text{g/mL}$) at 1 month post-Dose 3 (PD3) for each vaccination group.Objective: To assess the anti-PnPs serotype-specific IgG Geometric Mean Concentrations (GMCs) at 1 month PD3 for each vaccination group.	
Anti-PnPs serotype-specific IgG responses for the 15 serotypes contained in V114 at 1 month PD3Anti-PnPs serotype-specific IgG responses for the 15 serotypes contained in V114 at 1 month PD3

Objective: To assess the proportion of participants meeting threshold values* for protective responses to DTaP-IPV (Diphtheria toxin, Tetanus toxin, Pertussis toxin, Pertussis filamentous hemagglutinin (FHA), and Polio virus type 1/2/3) at 1 month PD3 for each vaccination group. Threshold value*: Diphtheria toxin level \geq0.1 IU/mL, Pertussis PT level \geq10 EU/mL Pertussis FHA level \geq10 EU/mL, Tetanus toxin level \geq0.01 IU/mL, Neutralizing antibody titers (NA) of Polio virus type 1/2/3 \geq1:8	
The antibody responses for DTaP-IPV at 1 month PD3
---	--

Overall Design:

Study Phase	Phase 1
Primary Purpose	Prevention
Indication	Pneumococcal disease
Population	Healthy Japanese infants
Study Type	Interventional
Intervention Model	Parallel This is a multi-site study.
Type of Control	Active control without placebo
Study Blinding	Double-blind
Masking	Participant or Subject Care Provider Investigator Sponsor
Estimated Duration of Study	The Sponsor estimates that the study will require approximately 2 years from the time the first participant signs the informed consent until the last participant's last study-related telephone call or visit. For purposes of analysis and reporting, the overall study ends when the Sponsor receives the last serology assay result or at the time of final contact with the last participant, whichever comes last.

Number of Participants:

Approximately 120 participants will be randomized (40 participants/group), estimating with 36 evaluable participants complete the study in each group.

Intervention Groups and Duration:

Intervention Groups	Intervention Groups and Duration						
	Intervention Group Name	Vaccine	Dose Strength	Dose Frequency	Route of Admin.	Vaccination Regimen	Use
V114-SC	V114	Refer to IB	4 doses	SC	Single dose at Visit 1, 2, 3 and 5* (Approximately 3, 4, 5, and 12 to 15 months of age).	Experimental	
V114-IM	V114	Refer to IB	4 doses	IM	Single dose at Visit 1, 2, 3 and 5* (Approximately 3, 4, 5, and 12 to 15 months of age).	Experimental	
PCV13-SC	PCV13	Refer to product labeling	4 doses	SC	Single dose at Visit 1, 2, 3 and 5* (Approximately 3, 4, 5, and 12 to 15 months of age).	Experimental	
Admin: Administration, PCV13: Pneumococcal 13-valent Conjugate Vaccine, IB: Investigator's Brochure, IM: Intramuscular, SC: Subcutaneous * DTaP-IPV (Diphtheria, tetanus, acellular pertussis, inactivated polio vaccine) is administrated with V114/PCV13 concomitantly at Visit 1, 2, 3 and 5.							
Total Number	3 intervention groups						
Duration of Participation	Each participant will participate in the study for approximately 10-14 months, from the time the parent/legal guardian signs the Informed Consent Form (ICF) through the final contact.						

Study Governance Committees:

Steering Committee	No
Executive Oversight Committee	No
Data Monitoring Committee	No
Clinical Adjudication Committee	No
Study governance considerations are outlined in Appendix 1.	

Study Accepts Healthy Volunteers: Yes

A list of abbreviations used in this document can be found in Appendix 8

1.2 Schema

The study design is depicted in [Figure 1](#).

[figure not shown]

Figure 1 V114-028 Study Design

1.3 Schedule of Activities (SoA)

Study Period	Screening						Notes
	Visit 1	Visit 2	Visit 3	Visit 4	Visit 5	Visit 6	
Visit Number							
Standard Age/ Scheduled Time	3 months	4 months	5 months	1 month PD 3	12~15 months	1 month PD 4	The age of the subject will fall within the appropriate age range for each trial visit.
	DOSE 1	DOSE 2	DOSE 3	POST DOSE 3	DOSE 4	POST DOSE 4	
Visit Window	3 months of age to 1 day prior to 4months of age	28 to 42 days after Visit 1	28 to 42 days after Visit 2	28 to 42 days after Visit 3	12 months of age to 1 day prior to 16 months of age	28 to 42 days after Visit 5	Months of age is calculated according to the participant's birth date.
Screening Procedures							
Informed Consent	X						Consent must be obtained before any study procedures.
Informed Consent for Future Biomedical Research (FBR)	X						Consent for FBR samples is optional and must be obtained before the collection of the buccal swab DNA samples.
Assignment of Screening Number	X						
Participant Identification Card	X						
Inclusion/Exclusion Criteria	X						
Medical History	X						The participant's medical history from the birth to first vaccination will be reviewed.
Post-enrollment procedures							
Assignment of Randomization Number	X						
Prior/Concomitant Medication and Nonstudy Vaccination Review	X	X	X	X	X	X	See Section 8.1.5 for details.

Study Period	Screening						Notes
	Intervention						
Visit Number	Visit 1	Visit 2	Visit 3	Visit 4	Visit 5	Visit 6	
Standard Age/ Scheduled Time	3 months	4 months	5 months	1 month PD 3	12~15 months	1 month PD 4	The age of the subject will fall within the appropriate age range for each trial visit.
	DOSE 1	DOSE 2	DOSE 3	POST DOSE 3	DOSE 4	POST DOSE 4	
Visit Window	3 months of age to 1 day prior to 4months of age	28 to 42 days after Visit 1	28 to 42 days after Visit 2	28 to 42 days after Visit 3	12 months of age to 1 day prior to 16 months of age	28 to 42 days after Visit 5	Months of age is calculated according to the participant's birth date.
V114 or PCV13 Administration (Blinded)	X	X	X		X		Due to differences in appearance, vaccine administration will be performed by unblinded trial personnel who will have no contact with study participants other than for administration of study vaccine. This includes all safety follow-up procedures (Section 6.3.3).
Concomitant Vaccine (DTaP- IPV) Administration	X	X	X		X		DTaP-IPV is administrated with V114/PCV13 concomitantly.
Nonstudy Pediatric Vaccines	(X)	(X)	(X)	(X)	(X)	(X)	Injectable vaccines should not be administrated in the same limb as the study vaccine.
Provide Vaccination Report Card (VRC)	X	X	X		X		See Section 8.1.9 for details.
VRC Collection		X	X	X		X	
Review VRC data		X	X	X		X	
Immunogenicity Procedures							
Collect Blood Samples for IgG Immunogenicity Assays	X*			X	X*	X	*Prior to vaccination
Collect Blood Samples for DTaP-IPV Immunogenicity Assays				X	X*	X	*Prior to vaccination

Study Period	Screening						Notes
	Intervention						
Visit Number	Visit 1	Visit 2	Visit 3	Visit 4	Visit 5	Visit 6	
Standard Age/ Scheduled Time	3 months	4 months	5 months	1 month PD 3	12~15 months	1 month PD 4	The age of the subject will fall within the appropriate age range for each trial visit.
	DOSE 1	DOSE 2	DOSE 3	POST DOSE 3	DOSE 4	POST DOSE 4	
Visit Window	3 months of age to 1 day prior to 4months of age	28 to 42 days after Visit 1	28 to 42 days after Visit 2	28 to 42 days after Visit 3	12 months of age to 1 day prior to 16 months of age	28 to 42 days after Visit 5	Months of age is calculated according to the participant's birth date.
Safety Procedures							
Full Physical Examination	X						To be performed by the investigator before vaccination to check inclusion/exclusion criteria/eligibility.
Targeted Physical Examination		X	X		X		To be performed by the investigator before vaccination.
Weight	X						
Body Temperature Measurement	X	X	X		X		Pre-vaccination body temperatures measured by site staff. (See section 8.3.2 for details)
30 Minutes Post Vaccination Observation Period	X	X	X		X		Subjects will be observed after study vaccination by blinded study personnel only.
AE Monitoring	←=====→						Nonserious AEs are to be reported from Days 1 through 14 following each vaccination. SAEs and deaths are to be reported throughout the duration of an individual's study participation.
Future Biomedical Research							
Collect Buccal Swabs for Future Biomedical Research	X						Collected from randomized participants who provided consent for FBR (Section 8.8)

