8.4 Adverse Events (AEs), Serious Adverse Events (SAEs), and Other Reportable Safety Events

The definitions of an AE or SAE, as well as the method of recording, evaluating, and assessing causality of AE and SAE and the procedures for completing and transmitting AE, SAE, and other reportable safety event reports can be found in Appendix 3.

Adverse events, SAEs, and other reportable safety events will be reported by the participant (or, when appropriate, by a caregiver, surrogate, or the participant's legally authorized representative).

The investigator and any designees are responsible for detecting, documenting, and reporting events that meet the definition of an AE or SAE as well as other reportable safety events. Investigators remain responsible for following up AEs, SAEs, and other reportable safety events for outcome according to Section 8.4.3.

The investigator, who is a qualified physician, will assess events that meet the definition of an AE or SAE as well as other reportable safety events with respect to seriousness, intensity/toxicity and causality.

8.4.1 Time Period and Frequency for Collecting AE, SAE, and Other Reportable Safety Event Information

All AEs, SAEs, and other reportable safety events that occur after the consent form is signed but before allocation/randomization must be reported by the investigator if they cause the participant to be excluded from the study, or are the result of a protocol-specified intervention, including but not limited to washout or discontinuation of usual therapy, diet, placebo treatment, or a procedure.

All AEs, SAEs, and other reportable safety events must be reported by the investigator from the day of allocation/randomization to the first vaccination and from the day of each vaccination through 14 days postvaccination. SAEs must also be reported throughout the duration of the individual's participation in the study, regardless of whether or not related to the Sponsor's product.

Additionally, any SAE brought to the attention of an investigator at any time outside of the time period specified in the previous paragraph also must be reported immediately to the Sponsor if the event is either:

1. A death that occurs prior to the participant completing the study.

OR

2. An SAE that is considered by an investigator who is a qualified physician to be vaccine-related.

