Investigators are not obligated to actively seek AEs or SAEs or other reportable safety events in former study participants. However, if the investigator learns of any SAE, including a death, at any time after a participant has been discharged from the study, and he/she considers the event to be reasonably related to the study intervention or study participation, the investigator must promptly notify the Sponsor.

All initial and follow-up AEs, SAEs, and other reportable safety events will be recorded and reported to the Sponsor or designee within the time frames as indicated in [Table 3](#).

Table 3 Reporting Time Periods and Time Frames for Adverse Events and Other Reportable Safety Events

Type of Event	Reporting Time Period: Consent to Randomization/Allocation	Reporting Time Period: Randomization/Allocation through Protocol-specified Follow-up Period	Reporting Time Period: After the Protocol-specified Follow-up Period	Time Frame to Report Event and Follow-up Information to Sponsor:
Nonserious Adverse Event (NSAE)	Report if: - due to protocol-specified intervention - causes exclusion - participant is receiving placebo run-in or other run-in treatment	Report all	Not required	Per data entry guidelines
Serious Adverse Event (SAE)	Report if: - due to protocol-specified intervention - causes exclusion - participant is receiving placebo run-in or other run-in treatment	Report all	Report if: - drug/vaccine related. - any death until participant completion of study (Follow ongoing to outcome)	Within 24 hours of learning of event
Pregnancy/Lactation Exposure	Not applicable since participants are infants.			Not applicable
Event of Clinical Interest	There are no ECIs for this study.			Not applicable
Cancer	Report if: - due to intervention - causes exclusion	Report all	Not required	Within 5 calendar days of learning of event
Overdose	Report if: - receiving placebo run-in or other run-in medication	Report all	Not required	Within 5 calendar days of learning of event

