8.12.2 Treatment Period/Vaccination Visit

Requirements during the treatment period/vaccination visit are outlined in Section 1.3.

If the participant develops a new clinical condition during the study that makes him/her ineligible for the study, the investigator should discuss with the Sponsor Clinical Director as soon as possible. The decision to continue the participant on study intervention requires the mutual agreement of the investigator, the Sponsor, and the participant's legally acceptable representative.

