In addition to individual events that occur in 4 or more participants in any vaccination group, AE summary measures (any AE, any vaccine-related AE, any SAE, any vaccine-related SAE, discontinuation of study vaccine due to an AE), and axillary temperatures (≥ 37.5 °C, ≥ 38.0 °C, ≥ 39.0 °C, ≥ 40.0 °C) collected from Day 1 through Day 7, will also be treated as Tier 2 events. For the purpose of the analysis of safety data in this study, an AE will be considered related to study vaccine if it is considered related to V114/PCV13 or DTaP-IPV.

Tier 3 events

Safety endpoints that are not Tier 1 or 2 events are considered Tier 3 events. Only point estimates by treatment group will be provided for Tier 3 safety parameters.

Table 5 Analysis Strategy for Safety Parameters

Safety Tier	Safety Endpoints	p-Value	95% CI	Descriptive statistics
Tier 1	Injection-site redness (Days 1 to 14) Injection-site swelling (Days 1 to 14) Injection-site hard lump (Days 1 to 14) Injection-site pain/tenderness (Days 1 to 14) Irritability (Days 1 to 14) Drowsiness (Days 1 to 14) Hives/welts (Days 1 to 14) Appetite loss (Days 1 to 14)	X	X	X
Tier 2	Any AE Any vaccine-related AE Any SAE Any vaccine-related SAE Discontinuation of study vaccine due to an AE Specific AEs or SOCs [†] (incidence ≥ 4 participants in any vaccination group) Axillary temperature (Days 1 to 7)		X	X
Tier 3	Specific AEs or SOCs [†] (incidence < 4 participants in all vaccination groups)			X

[†] Includes only those endpoints not pre-specified as Tier 1 or Tier 2.
X = Results will be provided.

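### A nonserious AE that starts after Day 14 and leads to a later dose being withheld need not be recorded, so the Tier 2 measure of AE-related vaccine discontinuation may undercount.

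*Combined protocol and SAP*

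**What the plan says.** **Collection.** The AE Monitoring note in the Schedule of Activities (Section 1.3) states: "Nonserious AEs are to be reported from Days 1 through 14 following each vaccination". Section 8.4.1 makes all AEs reportable from randomization to the first vaccination and then "from the day of each vaccination through 14 days postvaccination". It adds that "SAEs must also be reported throughout the duration of the" infant's participation. Table 3 in that section asks for all nonserious AEs in the period "Randomization/Allocation through Protocol-specified Follow-up Period" and none afterwards, without saying when that follow-up period ends.

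**Stopping vaccine.** Section 7.1 allows the investigator to discontinue study vaccine at any time for an untoward effect. Section 8.12.2 deals with illness arising between doses: "If the participant develops a new clinical condition during the study that makes him/her ineligible for the study", the investigator consults the Sponsor, and continuing needs the agreement of the investigator, the Sponsor and the infant's representative. Neither section has a 14-day limit.

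**Analysis.** Section 9.6.2 and sSAP 3.6.2 list "any vaccine-related SAE, discontinuation of study vaccine due to an AE" among the Tier 2 summary measures, which get between-group 95% CIs. The discontinuation item has no onset window and no data source. In the same table the Tier 1 items are labelled Days 1 to 14 and temperature Days 1 to 7. Separately, Section 9.6.3 and sSAP 3.6.3 display reasons for discontinuation by group, also without a window.

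**The concern.** The measure counts stops attributed to an AE, so it needs an AE to attribute them to. The decision whether to give the next dose can fall well after the reporting window has closed: 28 to 42 days after the previous dose for Doses 2 and 3, and many months after Dose 3 for Dose 4. Take an infant with a persistent rash that starts on Day 20 and is the reason the next dose is withheld. A site that reports exactly what is required enters no AE. The stop may then be missing from the Tier 2 table, or appear in disposition as AE-related with nothing to match it in the AE data.

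The primary objective is to describe safety and tolerability, and this is the summary measure that directly records AE-driven stopping. With 40 infants per arm, one uncounted case is 1/40 = 2.5 percentage points. If recording late AEs is left to each site, capture can vary by site behind a between-group comparison.

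**Working it through.** **Inputs.** From Section 1.3: Dose 1 from 3 months of age to 1 day before 4 months; Doses 2 and 3 each 28 to 42 days after the previous dose; Dose 4 from 12 months of age to 1 day before 16 months. The required nonserious-AE window is 14 days per dose. Section 9.9 gives 40 per arm. One month is taken as 30.44 days.

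**1. The plan's own figure.** Section 9.9 gives an 80% probability of seeing at least one event in 40 infants at a true incidence of 4%. Check: 1 − 0.96^40 = 0.805. It reproduces.

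**2. Dose 1 to 2 and Dose 2 to 3.** Share covered: 14/42 = 33% to 14/28 = 50%. Days not covered: 14 to 28 in each interval.

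**3. Dose 3 to 4.**
- Shortest: Dose 1 at the oldest age, both later intervals 42 days, Dose 4 at 12 months. (12 − 4) × 30.44 + 1 − 84 = 160.5 days; 14/160.5 = 9%.
- Longest: Dose 1 at 3 months, both intervals 28 days, Dose 4 at the end of its window. (16 − 3) × 30.44 − 1 − 56 = 338.7 days; 14/338.7 = 4%.

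**4. Dose 1 to 4.** 8 × 30.44 = 244 days to 13 × 30.44 = 396 days; the one-day offsets do not change the rounded shares. The windows do not overlap, so 3 × 14 = 42 days are covered: 42/396 = 11% to 42/244 = 17%. About 83 to 89% of the time in which a further dose could be withheld lies outside them. If the wording of Section 8.4.1 is read as one day longer per dose, 45 days give 45/396 = 11% to 45/244 = 18%.

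**5. What undercounting would do.** The documents give no share of AE-related stops that would be recorded, so this is an assumption, shown over a range. With a true incidence of AE-related discontinuation of 4% and captured share f, the chance of counting at least one in 40 is 1 − (1 − 0.04f)^40:

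| f (assumed) | Chance of counting at least one |
|---|---|
| 100% | 80% |
| 75% | 70% |
| 50% | 55% |
| 25% | 33% |

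**6. Is the gap closed elsewhere?** Nothing in Sections 7.1, 8.1.10, 8.4.1, 8.12.2 or 8.12.3 requires a nonserious AE to be reported because it led to discontinuation. Read widely, Table 3 would cover it, but that reading conflicts with the Schedule of Activities and the text of Section 8.4.1. Read narrowly, the gap stands.

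**The case against.** A reader might infer that a stop caused by a late nonserious AE cannot be counted at all. The documents do not support that. They set what must be reported and do not bar a later AE record. The measure itself has no day limit, and reasons for discontinuation are displayed by group, so a late AE-related stop can still appear in disposition. Section 6.4 also requires Sponsor consultation and written documentation when the vaccination plan is interrupted.

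Much of what would stop vaccination is captured already. SAEs are collected throughout, and Section 10.3.2 treats important medical events, including blood dyscrasias that do not lead to hospitalization, as usually serious. An AE that starts by Day 14 is recorded and followed under Section 8.4.3, so it counts even if it is Dose 4 that is withheld. The gap also ends at the Dose 4 visit, because no dose remains after it.

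A second tempting reading is that the measure captures only 11 to 17% of relevant events. That would need AE-related stops to arise at a constant rate between doses, and nothing in the documents says so. If reactions cluster early, the loss is much smaller. Nor do the documents show that any undercount differs between arms.

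All of this stands, and it limits the point. It does not remove it: optional recording is not a collection rule, the disposition display carries no between-group CI, and no rule reconciles the two tables.

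**Conclusion.** The concern holds in a limited form. The required reporting window is narrower than the period in which study vaccine can be stopped, and the Tier 2 measure has no definition that bridges the two. It may therefore undercount stops due to nonserious AEs that start after Day 14 following Doses 1 to 3, and may disagree with the disposition table.

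The gap is 83 to 89% of calendar time between Dose 1 and Dose 4. The number of missed events is unknown and may be small. The day counts rest on the visit windows and a 30.44-day month; the detection probabilities in step 5 rest on assumed capture shares.

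The measure is descriptive, and Section 9.6.2 itself says Tier 2 intervals are not a formal method of testing. The primary endpoints (solicited AEs to Day 14 and vaccine-related SAEs) are unaffected, and no sample-size or power figure changes. This is a cheap improvement, not a flaw in the trial's main conclusions.

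**What to change.** - In Section 8.4.1, Table 3 and the Schedule of Activities note, require reporting of any AE, serious or not, that leads to discontinuation of V114/PCV13 or DTaP-IPV, whatever its onset day, from Dose 1 up to the Dose 4 visit. In Table 3, also state when the follow-up period for nonserious AEs ends.
- In Section 9.6.2 and sSAP 3.6.2, state that the Tier 2 discontinuation measure counts these events regardless of onset day and is reconciled with the disposition reasons.
- Leave the other AE summaries on their current windows.

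The cost is a few sentences in the protocol and sSAP, a matching line in the data entry guidelines, and a few extra AE records, some of them for illness unrelated to vaccine. The change concerns what is recorded and counted, not when vaccine is stopped.

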2 INTRODUCTION

Merck Sharp & Dohme Corp. (MSD) is developing an investigational 15-valent pneumococcal conjugate vaccine (PCV) (referred to as V114) for the prevention of pneumococcal disease (PD) caused by the serotypes in the vaccine. V114 contains the 13 serotypes (1, 3, 4, 5, 6A, 6B, 7F, 9V, 14, 18C, 19A, 19F, 23F) present in the licensed vaccine PCV13 (pneumococcal 13-valent conjugate vaccine [diphtheria CRM₁₉₇ protein], Wyeth Pharmaceuticals, a subsidiary of Pfizer, Inc., Philadelphia, PA), plus 2 additional serotypes (22F, 33F).

